6.8.3.5 Management of Thyroid Toxicities

The use of cediranib has been associated with elevations of TSH and patients should be managed as per Table 15. In all cases, IPs should continue unless clinically contraindicated. Referral to an endocrinologist should also be considered if thyroid abnormalities occur.

Table 15 **Monitoring and Management of Thyroid Toxicities**

Result of TSH and FT4	Action
Increases of TSH with normal FT4	Monitor
Increases in TSH with normal FT4 and adverse events suggestive of incipient hypothyroidism	Consider replacement thyroxine
Increase in TSH with reductions in FT4	Consider replacement thyroxine

Abbreviations: FT4 free thyroxine; TSH thyroid stimulating hormone

6.8.3.6 Decrease in LVEF

Patients who have any of the following should undergo an echocardiogram (ECHO) or multigated acquisition (MUGA) scan at baseline and as clinically indicated (see [Table 5](#)) while on study:

- Prior treatment with anthracyclines
- Prior treatment with trastuzumab
- Prior central thoracic RT, including RT to the heart
- History of myocardial infarction within 6 to 12 months or history of other significant impaired cardiac function (Patients with history of myocardial infarction within 6 months are excluded from the study)

The decision to continue or interrupt cediranib/olaparib is based on the LVEF as it relates to the institution's LLN and change in ejection fraction from screening (LVEF as measured at enrollment) according to [Table 16](#).

Table 16 Monitoring and Management of Decreased LVEF

Relationship of LVEF to Institution's LLN at baseline	LVEF Decrease <10%	LVEF Decrease 10-15%	LVEF Decrease >15%
Normal	Continue	Continue	Continue and repeat MUGA/ECHO within 4-8 weeks
1-5% below LLN	Continue and repeat MUGA/ECHO within 4-8 weeks	Continue and repeat MUGA/ECHO within 4-8 weeks	Interrupt cediranib and repeat MUGA/ECHO within 3 weeks
> 6% below LLN	Continue and repeat MUGA/ECHO within 4-8 weeks	Interrupt cediranib and repeat MUGA/ECHO within 3 weeks	Interrupt cediranib and repeat MUGA/ECHO within 3 weeks

Abbreviations: ECHO echocardiogram; LLN lower limit of normal; LVEF left ventricular ejection fraction; MUGA multigated acquisition.
LVEF decreases in percentage points.

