 - History of myocardial infarction within 6 months prior to starting treatment
 - Unstable angina
 - Resting electrocardiogram (ECG) with clinically significant abnormal findings
 - New York Heart Association functional classification of III or IV.
15. Left ventricular ejection fraction (LVEF) $<$ lower limit of normal (LLN) per institutional guidelines, or $< 55\%$, if threshold for normal not otherwise specified by institutional guidelines, for patients with the following risk factors:
 - Prior treatment with anthracyclines

- Prior treatment with trastuzumab
 - Prior central thoracic RT, including exposure of heart to therapeutic doses of ionizing RT
 - History of myocardial infarction within 6-12 months prior to start of IPs
 - Prior history of other significant impaired cardiac function
16. History of stroke or transient ischemic attack within 6 months
 17. Uncontrolled intercurrent illness including, but not limited to known ongoing or active infection, symptomatic congestive heart failure, unstable angina pectoris, cardiac arrhythmia, extensive interstitial bilateral lung disease on High Resolution Computed Tomography (HRCT) scan or psychiatric illness/social situations that would limit compliance with study requirements.
 18. Patients with myelodysplastic syndrome (MDS)/treatment-related acute myeloid leukemia (t-AML) or with features suggestive of MDS/AML
 19. No prior allogeneic bone marrow transplant or double umbilical cord blood transplantation.
 20. Known active human immunodeficiency virus (HIV), Hepatitis B or Hepatitis C infection on antiviral treatment.
 21. Concomitant use of known strong cytochrome (CYP) 3A inhibitors (eg, itraconazole, telithromycin, clarithromycin, protease inhibitors boosted with ritonavir or cobicistat, indinavir, saquinavir, nelfinavir, boceprevir, telaprevir) or moderate CYP3A inhibitors (eg. ciprofloxacin, erythromycin, diltiazem, fluconazole, verapamil). The required washout period prior to starting study treatments is 2 weeks for strong inhibitors, and at least 1 week for moderate inhibitors.
 22. Concomitant use of known strong CYP3A inducers (eg, phenobarbital, enzalutamide, phenytoin, rifampicin, rifabutin, rifapentine, carbamazepine, nevirapine and St John's Wort) or moderate CYP3A inducers (eg. bosentan, efavirenz, modafinil). The required washout period prior to starting study treatments is 5 weeks for enzalutamide or phenobarbital and 4 weeks for other agents.

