3.9 Discontinuation of investigational product

Patients may be discontinued from IPs in the following situations:

- Patient decision; the patient is at any time free to discontinue treatment, without prejudice to further treatment. A patient who discontinues treatment is normally expected to continue to participate in the study unless she specifically withdraws her consent to further participation in any study procedures and assessments (see Section 3.10.1).
- Adverse Event (AE), including AEs that meet criteria for discontinuation as defined in Section 6.7; any AEs that, in the opinion of the Investigator or AstraZeneca, contraindicates further dosing.
- Objective progression according to RECIST version 1.1 criteria.
 - Severe non-compliance with the protocol

Both IPs (cediranib and olaparib) should be discontinued at the same time; patients are not allowed to remain in the study if they are taking either cediranib or olaparib as monotherapy.

However, in rare circumstances, patients experiencing ongoing clinical benefit but who develop one of the toxicities listed below, related to one of the IPs, that prevents them to continue to take this IP, may be allowed to continue on the unrelated drug if in the opinion of the treating investigator the risk benefit remains favorable and only after discussion with the AstraZeneca Study Physician and the Principal Investigator.

AEs requiring cediranib to be discontinued:

- GI perforation
- Arterial Thromboembolic Event
- Reversible Posterior Encephalopathy Syndrome (PRES)
- Severe hemorrhage
- Severe persistent hypertension despite maximal anti-hypertensive treatment

AEs requiring olaparib to be discontinued:

- Bone marrow findings consistent with MDS/AML.
- Severe persistent anemia
- Pneumonitis

Refer to Section 6.7 for more information on the management of IP-related toxicities.

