- m. Left Ventricular Ejection Fraction required for patients with prior treatment with anthracyclines, or prior treatment with trastuzumab or central thoracic radiation therapy (RT) including exposure of heart to therapeutic doses of ionizing RT, history of myocardial infarction within 6-12 months prior to enrolment or history of other significant impaired cardiac function. For these patients LVEF will be done at screening and thereafter as clinically indicated, and per recommendations following review of initial safety data by the sponsor (see Table 16).
- n. At screening, UPC ≤ 1 , OR proteinuria $\leq 2+$ on two consecutive dipsticks taken no less than 1 week apart, is required. Patients with 2+ proteinuria on dipstick must also have UPC < 0.5 on 2 consecutive samples. Refer to Section 5.2.1.4 for information on management of patients with potential nephrotic syndrome.
- o. Repeat assessment not required on Day 1, if already performed during previous 7 days for screening purposes.
- p. Full Blood Count as per Section 5.2.1.1: hemoglobin, platelets, mean cell volume, white blood cell count, absolute neutrophil count and absolute Lymphocyte count
- q. Biochemistry (sodium, magnesium, calcium, potassium, albumin, total protein, creatinine, total bilirubin, AL.T, AST, alkaline phosphatase). Creatinine clearance (Cockcroft-Gault or another validated method); to be calculated at baseline and re-calculated as clinically indicated during study conduct.
- r. Baseline tumor assessment should include CT/MRI of the chest, abdomen and pelvis. Follow-up CT/ MRI tumor assessments will cover chest (in those patients with disease in the chest or upper abdomen lymphadenopathy at baseline), abdomen and pelvis. Any other sites at which new disease is suspected should also be appropriately imaged. Baseline radiological imaging is required within 4 weeks prior to first dose of investigational products (IPs). Follow up assessments should be done every 8 weeks after first dose of IP until objective radiological disease progression, withdrawal of consent or the primary analysis.
- s. Blood samples for PBMC testing (8 mL) and plasma biomarker testing (6 mL) will be taken at baseline; at Week 4; at Week 8 and treatment discontinuation. Details to be found in the lab manual.

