6.8 Management of IP related toxicities

The dose levels and the general approach to dose modification of the cediranib and olaparib component of the combination therapy are shown in Table 7 and Table 8, respectively. Specific dose modification information for some AEs are provided in Section 6.8.3 and Section 6.8.4. Please refer to the current IBs for emerging safety data for cediranib and olaparib: CCI

AEs should be treated with the appropriate maximum supportive care, and dose reductions should be clearly documented in the eCRF.

Table 7 Dose modification cediranib

Dose Level	Cediranib tablets
Initial dose	30 mg daily
Dose reduction 1	20 mg daily
Dose reduction 2	15 mg daily

Table 8 Dose modification of olaparib

Dose Level	Olaparib tablets
Initial dose	200 mg twice daily
Dose reduction 1	150 mg twice daily
Dose reduction 2	100 mg twice daily

At the discretion of the investigator, the study drugs may be held or dose modified independently if the observed toxicity is attributed to only one of the drugs, while the patient continues to receive the drug not associated with the observed toxicity. The time a given drug is held should not exceed 3 weeks. Once dose of study drug(s) have been reduced, no dose re-escalation is permitted.

If treatment has to discontinue due to toxicity, both IPs (cediranib and olaparib) should be discontinued at the same time; patients are not allowed to remain in the study if they are taking either cediranib or olaparib as monotherapy. However, in rare circumstances, patients experiencing ongoing clinical benefit but who develop one of the toxicities listed below related to one of the IPs that prevents them to continue to take this IP, may be allowed to continue on the unrelated drug if in the opinion of the treating investigator the risk benefit remains favorable and only after discussion with the AstraZeneca Study Physician and the Principal Investigator.

AEs requiring cediranib to be discontinued:

- GI perforation
- Arterial Thromboembolic Event
- PRES
- Severe hemorrhage
- Severe persistent hypertension despite maximal anti-hypertensive treatment

AEs requiring olaparib to be discontinued:

- Bone marrow findings consistent with MDS/ AML
- Severe persistent anemia
- Pneumonitis

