6.8.2 Non-hematologic toxicity

Cediranib should be discontinued should any of the following AEs occur: GI perforation; arterial thromboembolic events; PRES (radiologically confirmed); severe or medically significant hemorrhage and severe persistent hypertension despite maximal anti-hypertensive treatment.

Dose modifications for other non-hematologic events on IPs should be managed according to Table 11.

Table 11 General Management of Non-Hematologic Toxicity

Observation	Action
AE resolves promptly with supportive care	Maintain dose level
Any \geq Grade 3 non-hematologic (excluding grade 3 fatigue or easily correctable asymptomatic grade 3 laboratory abnormalities)	Hold IP(s) ^a for up to 3 weeks until toxicity resolves to \leq Grade 1. Treatment may be restarted at one dose level lower for the IP(s) causing the toxicity (see Table 7 and Table 8), at the treating investigator's discretion ^b . Reoccurrence of Grade 3 or 4 toxicity would require dose reduction of both IPs.
Any grade 2 non-hematologic AE or grade 3 fatigue related to cediranib or olaparib that persists despite maximal support.	Hold IP(s) ^a for up to 3 weeks until toxicity resolves to Grade ≥ 1 . Treatment may be restarted at one dose level lower for the IP(s) causing the toxicity (see Table 7 and Table 8), at the treating investigator's discretion ^b .
Grade 3 or 4 non-hematologic AE related to cediranib and olaparib combination that does not resolve to Grade 0-2 within 3 weeks despite maximum supportive care after treating patient at the lowest reduced dose level ^c	Discontinue IP(s)

a. At the discretion of the investigator, one IP may be held or dose modified or discontinued independently if the observed toxicity is attributed to only one of the drugs, while the patient continued to receive the second drug not associated with the observed toxicity. The time a given drug is held should not exceed 3 weeks.

- b. Patients who are at the lowest reduced dose level may have their drug resumed at that dose level after discussion with the AstraZeneca Study Physician and the Principal Investigator if evidence of clinical benefit.
- c. For venous thromboembolic events, treatment may be resumed at the discretion of the investigator once patient is asymptomatic (Section 6.7.3.11).

Abbreviations: AE adverse event; IP investigational product(s)

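### Table 16 sets its rows by LVEF at baseline, so correctly enrolled patients with a required screening LVEF can never reach an instruction to interrupt cediranib

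*Protocol*

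**What the plan says.** **The rule.** Protocol 6.8.3.6 says that the decision to continue or interrupt "is based on the LVEF as it relates to the institution's LLN and change in ejection fraction from screening". A parenthesis identifies the screening value as the LVEF measured at enrolment. It is attached to the change term, not to the comparison with LLN.

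**The table.** Table 16 carries out that rule. Its columns are the fall in LVEF in percentage points (under 10, 10 to 15, over 15). Its rows are headed "Relationship of LVEF to Institution's LLN at baseline", with three bands: normal, 1-5% below LLN, and more than 6% below LLN.

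**Who is scanned.** Table 5 footnote m requires LVEF in patients with prior anthracyclines, trastuzumab or central thoracic radiotherapy, a myocardial infarction 6 to 12 months earlier, or other significant cardiac impairment. "For these patients LVEF will be done at screening and thereafter as clinically indicated".

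**Who is enrolled.** Exclusion 15 (section 3.2) bars LVEF below the institutional LLN, or below 55% "if threshold for normal not otherwise specified by institutional guidelines, for patients with the following risk factors". Its list is essentially the same as that in footnote m. Section 3 allows no exceptions to eligibility.

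**Where sites look.** Section 6.8 states: "Specific dose modification information for some AEs are provided in Section 6.8.3 and Section 6.8.4". Table 16 lies within 6.8.3.

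**The concern.** The heading and exclusion 15 together close off most of the table. If the row is fixed by the baseline value, and eligibility requires that value to be at or above LLN in exactly the patients who must have a baseline scan, the two lower rows do not apply to the group that the section covers. A section written to decide between continuing and interrupting would then never interrupt for them, however far LVEF fell.

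The same scan therefore leads to different dosing depending on how a site reads one heading. These patients are selected for testing because of cardiac risk, and section 6.1.1 lists symptomatic left ventricular dysfunction and cardiac failure as adverse events of special interest for cediranib. The study has no Data Monitoring Committee (section 1.5.2). The dose-modification rules also stay in force for patients who continue treatment after the Final Protocol Visit (section 4.5).

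**Working it through.** The plan gives no figure to reproduce. The check applies Table 16 under each reading of its row heading.

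**Table 16 as a lookup** (F = fall from screening, in percentage points)

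| Row | F under 10 | F 10 to 15 | F over 15 |
|---|---|---|---|
| Normal | continue | continue | continue, repeat in 4-8 weeks |
| 1-5 below LLN | continue, repeat in 4-8 weeks | continue, repeat in 4-8 weeks | interrupt cediranib, repeat in 3 weeks |
| more than 6 below LLN | continue, repeat in 4-8 weeks | interrupt cediranib, repeat in 3 weeks | interrupt cediranib, repeat in 3 weeks |

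**Reachable cells, row set by baseline.** Exclusion 15 requires screening LVEF at or above LLN, so only the Normal row applies. That leaves 3 of 9 cells reachable and none of the 3 interrupt cells.

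**Reachable cells, row set by on-study LVEF.** All 9 cells can occur, including all 3 interrupt cells.

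**Worked cases.** LLN is 55% (the default in exclusion 15) and screening LVEF is assumed to be 60%.

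| On-study LVEF | Fall | Below LLN | Row by baseline | Row by on-study value |
|---|---|---|---|---|
| 45% | 60 - 45 = 15 | 55 - 45 = 10 | continue, no repeat scan | interrupt |
| 40% | 60 - 40 = 20 | 55 - 40 = 15 | continue and repeat | interrupt |
| 49% | 60 - 49 = 11 | 55 - 49 = 6 | continue, no repeat scan | no row; adjacent rows give continue-and-repeat and interrupt |

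**Whole grid.** Take LLN 55, every whole-number screening LVEF from 55 to 75, and every on-study value from 20 up to the screening value. The number of pairs is the sum of (screening - 19), which runs from 36 to 56 over 21 screening values: 21 × 46 = 966.

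- Row by baseline: 0 of 966 pairs interrupt.
- Row by on-study value, 48 or lower with a fall of at least 10: 26 + 27 + 28 for screening 55, 56 and 57, then 29 for each of the 18 values 58 to 75 (522). Total 603.
- Row by on-study value, 50 to 54 with a fall over 15: 1 + 2 + 3 + 4 + 5 for screening 66 to 70, then 5 for each of 71 to 75 (25). Total 40.
- Interruptions on the on-study reading: 603 + 40 = 643.
- Of those 643, the baseline reading gives plain continuation in 39 (on-study 48 or lower, fall 10 to 15: 6+6+6+6+5+4+3+2+1). It gives continuation with a repeat scan in the other 643 - 39 = 604.
- On-study LVEF of exactly 49 has no row: 21 pairs, one per screening value.

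**Wider grid.** With on-study values down to 10 and a value 6 points below LLN placed in the lowest row, the baseline reading gives 0 interruptions of 1176 pairs (LLN 55) and 0 of 1391 (LLN 50). The on-study reading gives 870 and 965.

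These are counts of combinations, not probabilities for patients.

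**The case against.** **The wording is ambiguous rather than contradictory.** The sentence above the table gives no time point for the comparison with LLN and never says current or on-study. With some strain, the words at baseline could qualify the institution's LLN, and the table then works. It is true that the documents do not settle the intended meaning. But the sentence attaches the enrolment value to the change alone, and only the on-study reading makes the lower rows usable in this group. If that reading was meant, the heading should say so.

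**The lower rows are not void for everyone.** A patient without the risk factors who happens to have a baseline scan, or one enrolled in error and kept on treatment (section 3.4.2), could fall in them. That is correct, and the finding does not extend to those patients.

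**Other safeguards remain.** "Dose modifications for other non-hematologic events on IPs should be managed according to Table 11": Table 11 holds drug for Grade 3 or higher events, with limited exceptions, and for related Grade 2 events that persist despite maximal support. At the investigator's discretion "the study drugs may be held or dose modified independently if the observed toxicity is attributed to only one of the drugs", and section 3.9 permits stopping for any event that "in the opinion of the Investigator or AstraZeneca, contraindicates further dosing". Events of special interest need close monitoring and rapid communication to the sponsor. On-study scans are done when clinically indicated or on sponsor recommendation after safety review (footnote m), so a clinician will often already be concerned. All of this stands, and nothing forbids a hold. However, Table 11 works by CTCAE grade and the documents give no LVEF cut-offs for those grades, so it cannot be shown to act at the same values. Table 16 is the specific rule that a site would look up.

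**The sharpest contrast is the less common one.** In 604 of the 643 discordant combinations the heading still calls for a repeat scan. That is right, but a repeat in 4 to 8 weeks while dosing continues is not the same as interruption.

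**The gaps in the bands matter little.** Fractional gaps matter only if sites report fractional LVEF. The gap at exactly 6 points arises with whole numbers, but it is secondary.

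**Conclusion.** The concern holds. Followed as headed, Table 16 cannot produce an interruption of cediranib in a correctly enrolled patient with a protocol-required screening LVEF: 6 of its 9 cells, including all 3 interrupt cells, are out of reach.

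The reachability result needs only exclusion 15 and the heading, and holds for any LLN. The worked cases assume LLN 55% and screening LVEF 60%, and read the row bands as percentage points; the table's footnote states that unit only for the decreases. That on-study LVEF was intended is an inference from the sentence above the table.

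The documents do not say how many of the approximately 60 patients carry the risk factors, so the number affected is unknown. The point concerns safety conduct; no efficacy endpoint definition depends on it. Because general holding rules remain, this should be fixed but does not invalidate the study.

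**What to change.** 1. Change the row heading to the relationship of current on-study LVEF to the institution's LLN. Keep the columns as the percentage-point fall from screening.
2. Make the bands contiguous: at or above LLN; below LLN by less than 6 points; below LLN by 6 points or more. The sponsor's physicians should confirm the exact cut.
3. Send sites a clarification letter with the corrected table.

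**Cost.** One heading, three row labels and a letter to approximately 40 sites. No new type of procedure is added beyond the repeat scans already in the table. If the sponsor classes the correction as substantial, section 10.5 requires a protocol amendment with ethics committee or IRB approval before it takes effect.

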6.8.3.7 Posterior Reversible Encephalopathy Syndrome (PRES)

Posterior reversible encephalopathy syndrome (PRES) has been uncommonly reported in clinical studies with cediranib. PRES is a neurological disorder which can present with headache, seizure, lethargy, confusion, blindness and other visual and neurologic disturbances, and can be fatal. Mild to severe hypertension may be present. In patients developing PRES, treatment of specific symptoms including control of BP is recommended. Confirmation of PRES requires brain imaging, preferably MRI. Cediranib should be discontinued following confirmation of PRES. The safety of reinitiating cediranib in patients previously experiencing PRES is not known.

6.8.3.8 Gastrointestinal perforation

GI perforation has been uncommonly reported in cediranib treated patients and may be fatal. Cediranib should be used with caution in patients at risk and permanently discontinued in patients who develop GI perforation.

6.8.3.9 Fistula

In patients treated with cediranib, fistula has been reported and reflected the location of the underlying malignancy. In the ovarian cancer population, vaginal fistula has been uncommonly reported in cediranib treated patients. Cediranib should be used with caution in patients at risk of fistula and discontinuation of cediranib should be considered in patients who develop fistulae.

